6.2 Data management

The REDCap database is used for digital data collection. Each study participant will be assigned a six-digit identification number (ID) for anonymization purposes. Personal data will only be stored in ID-encrypted form. The password-protected master list, which contains the assignment of IDs to personal data, ensures that personal data can be deleted when the study is completed. The master list is stored on a secure data server at the Paracelsus Medical University of Salzburg and is only accessible to the researcher responsible for recruitment, eligibility checks and allocation. Data from medical examinations and surveys are stored in spreadsheet files. Only authorized researchers have access to the data. Participants can access their personal data after completion of the study.

Written consent will be obtained from all study participants for the use of their personal data. The consent forms will include a specific clause on the protection of personal data, informing study participants of how their data will be handled and stored, the purpose of the research, the contact details of the data protection officer and their rights.

All personal data will be handled as defined in General Data Protection Regulation (EU 2016/679), and Finnish Data Protection Act 1050/2018.

Each person involved in the conduct of the study (hiking guides, assistants, etc.) will sign a confidentiality agreement before the start of the study, which will be countersigned by the principal investigator of the study. Confidentiality refers to all circumstances that become known through participation in the study, in particular information about study participants, employees and other cooperation partners regarding economic, operational, technical, tax and personal circumstances as well as internal matters of any kind.

The data will be used for scientific purposes and for possible publication in scientific journals and conferences. In addition, the results of the study will be used for the further development and implementation of effective, sustainable and cost-effective nature-based therapies (including health equity, nature conservation and health economics aspects).

Saliva samples from the Padua (NATURE-MET-P) and Barcelona (NATURE-MET-B) studies will be sent to the Paracelsus Medical University for analysis. The probes will only be labelled with an identification number (ID), so the analysis will be completely anonymous and experimenter-blinded.

The blood and saliva samples will be stored in a video-monitored and locked room (Paracelsus Medical University Salzburg, House C, [name]) in a freezer at -80°C until analysis. After analysis, the samples will be stored until publication(s). Storage of the samples until publication(s) is necessary in order to fulfil any requests from the journal and to allow for any minor or major revisions.

The NATURE-MET-S study is part of the HORIZON EUROPE project RESONATE⁷. A total of nine studies, including 5 randomized controlled trials, are being carried out within this project. The RESONATE project is structured in such a way that the case studies will not only collect data relevant to their own research question, but also data needed for the tasks of different work packages (WPs) within the project (e.g. health equity

⁷ RESONATE: Building individual and community resilience through nature-based therapies, Project Nr. 101081420; Resonate (resonate-horizon.eu)

aspects, nature conservation aspects, process evaluation). As a visual aid, please see Figure 3.

[figure not shown]

Figure 3: Case study collaboration

The collected data will be transferred via the scientific database system RedCap to a secure server at the University of Vienna (lead partner of the RESONATE project). From there, the data will be distributed to the respective work package leaders via the REDCap database system according to the RESONATE data management plan⁸.

Data protection officer at the University of Vienna (RESONATE Lead Partner):

Contact: [contact]

Requests for information in accordance with Article 15 of the EU General Data Protection Regulation (GDPR): [contact]

Data protection [contact]

⁸ see draft of attached RESONATE data management plan

6.3 Statistics

All statistical analyses will be performed using the R-GNU software environment (General Public License, R Foundation for Statistical Computing, Vienna, Austria) and SPSS (IBM). Statistical significance will be set at the level of a < 0.05 for all tests. Randomly missing values will be replaced using the standard procedure, last outcome carried forward (LOCF). The statistical analysis will be carried out by a biometrician. The data will be blinded again in order to exclude a possible bias with regard to an expected result.

Statistical analyses will be performed in accordance with the intention-to-treat principles and reporting will adhere to the CONSORT-statement, including CONSORT flow chart (Calvert et al., 2013; CONSORT, 2019).

After a positive vote, the study will be preregistered in the ISRCTN registry (https://www.isrctn.com/).

Check for normal distribution

The Shapiro-Wilk test will be applied to check for normal-distribution. Depending on data distribution, parametric or non-parametric tests will be applied.

Analysis of Baseline values

To analyze possible baseline differences between the two groups, a t-test for unconnected samples is performed for normally distributed variables and a Mann-Whitney Utest for non-normally distributed parameters. Nominally scaled variables are analyzed using the chi-square test. If any baseline variables are significantly different between the groups, secondary analysis will be conducted including these variables to adjust for any residual confounding not prevented by the randomization.

Longitudinal Data analysis

Depending on data distribution, parametric or non-parametric tests will be applied. Participant data will be compared in terms of baseline data, including outcome variables as well as demographics (unpaired Student-T-Test or Wilcoxon-test).

For longitudinal data analysis, analyses of variance (ANOVA) or linear mixed models (LMM) are used for normally distributed data.

For non-normally distributed samples, a non-parametric analysis of variance (e.g. f1.LD.f1) is performed using the nparLD package (Noguchi et al., 2012).

Models will include random effects for temporal and spatial correlations and fixed effects for: (1) intervention group; (2) time effects characterizing changes between pre- and post-intervention; and (3) interaction between the intervention group and the pre- and

post-intervention temporal effects, representing the group contrast. This determines whether or not the intervention has an effect. If any baseline variables are significantly different between the groups, secondary analysis will be conducted including these variables to adjust for any residual confounding not prevented by the randomization.

Multiple testing:

We will adjust for multiple testing, e.g., Benjamini-Hochberg or Holm-Bonferroni.

7 Methods: Data monitoring

The responsibility for the complete and correct data collection and documentation as well as the safe storage of the data in the context of the clinical study lies with the staff of the Paracelsus Medical University and the University Clinic for Internal Medicine I of the University Hospital Salzburg.

Data will only be shared with the RESONATE Lead Partner in an ID-encrypted form and in accordance with the RESONATE Data Management Plan (see chapter 6.2 Data management).

Data collection and storage is implemented in such a way as to minimize the possibility of inaccurate, erroneous and/or incomplete data entry. Entries and corrections can only be made by authorized persons. All entries and corrections are dated, documented and traceable or recoverable.

Internal audits shall be conducted at least three times: (1) prior to the start of the clinical trial, (2) during the conduct of the clinical trial and (3) after the completion of the clinical trial. The following activities are planned as part of the internal audits:

- Verification that the trial site meets the requirements of the clinical trial, e.g. requirements for the trial population, equipment, storage of trial materials.
- Comparison of source data
- Verification of proper and safe storage of samples

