4.4 Outcome parameters

4.4.1 Primary endpoints

The primary endpoint of the present clinical study is the effect of the intervention on biopsychosocial resilience (White et al., 2023), quantified in relation to MetS by recording following parameters. (see also Figure 1 for definition of time points) :

I. Primary endpoints t1-t3

1) Health-related quality of life (SF-12) (Weinhardt & Richter, 2013)

Health-related quality of life is measured by the German version of the Short Form Health Survey SF-12. The SF-12 measures health-related quality of life in two summary scales (physical health (PH) and mental health (MH)) (Weinhardt & Richter, 2013). This means that the SF-12 can map the two summary scales of the SF-36. However, the SF-12 consists of only 12 items and can therefore be completed in less time (Y. Lin et al., 2020; Ware & Gandek, 1998; Wee et al., 2008). The total scale ranges from 0 to 100 points, with higher scores reflecting better quality of life (Ware & Gandek, 1998).

The threshold for a clinically significant change in QoL should always be considered in relation to the change in other parameters (e.g. ALI) (Ware et al., 1995). In general, a change of 2.5-5.0 points on a summary scale is considered clinically relevant (Fan et al., 2004).

In the present study, a change in the SF-12 total score of 2.5 points or more is therefore defined as a clinically relevant change.

2) Allostatic Load

- a. Allostatic Load Index 1 (derived from: (Adams-Campbell et al., 2021; McCrory et al., 2023):
 - Dehydroepiandrosterone sulfate (DHEA-S)
 - Heart rate variability (HRV)
 - Systolic and diastolic blood pressure
 - Resting heart rate
 - Peak Expiratory Flow (PEF)
 - HDL Cholesterol
 - LDL Cholesterol
 - Triglycerides
 - HbA1C
 - Waist-hip ratio
 - C-reactive protein (CRP)
 - Interleukin-6
 - TNF-alpha
- b. Allostatic Load Index 2 (experimental, non-invasive):
 - Dehydroepiandrosterone sulfate (DHEA-S) from saliva
 - Heart rate variability (HRV)
 - Systolic and diastolic blood pressure
 - Resting heart rate
 - Peak Expiratory Flow (PEF)
 - Waist-hip ratio
 - C-reactive protein (CRP) from saliva

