4.6 Sample size

The calculation of the sample size is based on published study results from the Institute of Ecomedicine. The study investigated the effect of nature-based therapy on individuals with sedentary lifestyles. (Huber et al., 2023; Pichler et al., 2022, ISRCTN43292449 https://doi.org/10.1186/ISRCTN43292449):

- Study type: two-armed randomized controlled clinical trial
- Intervention: nature-based therapy (mindfulness-based forest therapy vs. hiking; Forest vs. Hiking)
- Outcome parameter for sample size calculation: health-related quality of life (SF-12)
- Study population: 50-60 years, sedentary lifestyle, moderate overweight (BMI ≥25–≤30)

The sample size was calculated with a bootstrap simulation (using the software R-GNU, Genal Public License, R Foundation for Computing), applying the F1-LD-F1 model from the nparLD package (Nonparametric Longitudinal Data Analysis) (Noguchi et al., 2012). The initial seed for the variate generator was set at 1 and the re-sampling process was fixed to 1000 repetitions for each sample size. The percentage of significant results was used as an estimator of power.

Regarding clinical studies on lifestyle interventions in overweight individuals, recent literature reports dropout rates ranging from 30% to 50% (Collins et al., 2022; Ruelas et al., 2023).

A drop-out and lost-to-follow-up rate (until T4 = day 180) of 40 % was assumed for the present study, resulting in a sample **size of n=70 per study arm**.

Sample size	Туре	FALSE	TRUE	Power	Comparison
10	nparLD	698	302	0,302	FoHi
20	nparLD	485	515	0,515	FoHi
30	nparLD	316	684	0,684	FoHi
40	nparLD	183	817	0,817	FoHi
50	nparLD	127	873	0,873	FoHi
60	nparLD	58	942	0,942	FoHi
70	nparLD	38	962	0,962	FoHi
80	nparLD	18	982	0,982	FoHi
90	nparLD	11	989	0,989	FoHi
100	nparLD	3	997	0,997	FoHi

Table 1: Sample size calculation based on Huber et al., 2023

FoHi = Forest vs. Hiking

[figure not shown]

Figure 2: Sample size calculation based on Huber et al., 2023

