4.7 Recruitment

The clinical study will recruit a total of 140 participants, with 70 in each study arm. The University Clinic for Internal Medicine I of the Salzburg University Hospital (study center 2) will conduct clinical inclusion, while the Institute for Ecomedicine of the Paracelsus Medical University Salzburg (study center 1) will carry out the intervention.

Study participants can register for the study through the Paracelsus Medical University website (primary source, www.pmu.ac.at/ecomedicine).

A total of 140 study participants are recruited through the following channels:

1) Paracelsus 10,000 data base

People with metabolic syndrome aged between 40 and 65 years will be identified from the database of the Paracelsus 10,000 Study(Frey et al., 2021). A sample of n=500 people, stratified by age and sex, will then be selected from these data and informed by post about the possibility of participating in the study.

2) University clinic for internal medicine I of the Salzburg University Hospital

In addition, recruitment will take place via the outpatient clinics (metabolic, diabetes, obesity) of the University Clinic for Internal Medicine I of the University Hospital Salzburg (head physician: Univ. [name]. [name]; active approach of eligible persons, website, distribution of information material).

3) Resident general practitioners and internists

Information material about the study will be sent to local internists and general practitioners (GPs) in the city of Salzburg and surrounding communities to make eligible patients aware of the opportunity to participate in the study.

The design and content of the digital and analog advertising material are identical.

The communication of the clinical study and the recruitment of study participants will be carried out in compliance with the guidelines for advertising study participation of the Ethics Commission of the Federal State of Salzburg.

An online questionnaire will be used for enrolment and an initial assessment of the inclusion and exclusion criteria. The data collected during registration will be stored on a secure server at the Paracelsus Medical University of Salzburg and will only be used to contact participants and assess their eligibility. The data will be deleted after recruitment is completed.

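### Section 6.3 fills missing values by last outcome carried forward, which can bias the group-by-time contrast in either direction even when data are missing at random, in a trial that plans for 40% loss by day 180

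*Protocol*

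**What the plan says.** Section 6.3 gives one rule for missing data, placed ahead of all the analyses: "Randomly missing values will be replaced using the standard procedure, last outcome carried forward (LOCF"). The protocol names no other method, no sensitivity analysis, and no rule for values that are not randomly missing. The same section adopts intention-to-treat and takes the interaction of group with time as the treatment effect. Its longitudinal methods depend on distribution. For normal data it offers ANOVA as one option, and as the other "linear mixed models (LMM) are used for normally distributed data". Otherwise it uses nparLD. On significance it says: "Statistical significance will be set at the level of a < 0.05 for all tests".

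On expected loss, section 4.6 says that "recent literature reports dropout rates ranging from 30% to 50" per cent, and then: "A drop-out and lost-to-follow-up rate (until T4 = day 180) of 40 % was assumed for the present study". This leads to a "size of n=70 per study arm", repeated in section 4.7 ("with 70 in each study arm"). Section 4.4.1 places the SF-12 and ALI endpoints at t1 to t3. Section 4.5 dates T3 at day 70.

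**The concern.** Carrying the last value forward fixes a participant's outcome at the moment of loss. Someone lost before T2 enters the contrast with a change of exactly zero, and someone lost between T2 and T3 enters T3 with the T2 value. Calling the missing values random does not make this true. Randomness describes who goes missing, not what happens to them afterwards.

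Four things could follow:
- An effect that builds up is diluted.
- An effect that fades after T2 is partly reported at T3.
- If both arms improve but one loses more people, a difference appears where none exists.
- Imputed values count as observed information about T3.

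Unequal loss is possible here: the trial is open, with a waiting-list control. The mixed model named in the same section needs no such assumption. It uses every observed visit and is valid under missing at random.

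This is not a detail left for a later analysis plan. The protocol prescribes the method, and an analysis plan that avoided it would contradict the protocol.

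**Working it through.** **Inputs from the protocol.** There are 70 per arm and 40% loss by day 180. At day 180 that is 0.40 × 70 = 28 lost and 42 remaining per arm. The SF-12 relevance threshold is 2.5 points: "a change in the SF-12 total score of 2.5 points or more is therefore defined as a clinically relevant change". Alpha is 0.05; two-sided testing is assumed.

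**Assumptions, because the protocol gives no figures.** SD 10 and correlation 0.6 between any two visits. Loss by T3 is 20% or 40%, with the same hazard in both intervals. Mean changes at T2 are half those at T3, except in the fading case. The plan has no figure of its own on this point to reproduce.

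**Formula.** Let L be the loss by T3. The share still present at T2 is √(1−L). The share lost between T2 and T3 is p = √(1−L) − (1−L). If loss does not depend on scores, the expected carried-forward mean change in an arm is p × (mean change at T2) + (1−L) × (mean change at T3). Those lost before T2 add zero.
- L = 0.40: √0.60 = 0.775, p = 0.175, completers 0.600.
- L = 0.20: √0.80 = 0.894, p = 0.094, completers 0.800.

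**Growing effect, 1.25 at T2 and 2.5 at T3, equal loss.**
- 40%: 0.175 × 1.25 + 0.600 × 2.5 = 1.72.
- 20%: 0.094 × 1.25 + 0.800 × 2.5 = 2.12.

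Simulation with loss that depends on the last observed score (missing at random) gives the same 1.7 and 2.1. A likelihood-based analysis of the same data gives 2.5.

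**Fading effect, 5 at T2 and 0 at T3, equal loss.**
- 40%: 0.175 × 5 = 0.88.
- 20%: 0.094 × 5 = 0.47.

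The truth at T3 is 0, and the rule reports about 0.5 to 0.9.

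**No effect, both arms improve by 2 at T2 and 4 at T3, unequal loss.** The expected mean change by loss rate is:

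| Loss by T3 | p | Carried-forward mean change |
|---|---|---|
| 10% | 0.049 | 0.049 × 2 + 0.90 × 4 = 3.70 |
| 15% | 0.072 | 0.072 × 2 + 0.85 × 4 = 3.54 |
| 25% | 0.116 | 0.116 × 2 + 0.75 × 4 = 3.23 |
| 30% | 0.137 | 0.137 × 2 + 0.70 × 4 = 3.07 |
| 50% | 0.207 | 0.207 × 2 + 0.50 × 4 = 2.41 |

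The false differences are 0.31 (15% against 25%), 0.63 (10% against 30%) and 0.66 (30% against 50%) when loss is unrelated to scores. When people with poor scores leave more often, simulation gives about 0.4 to 1.0. The type I error is then about 6% (15% against 25%) to 10% (the other two pairs). Both grow as loss follows the score more closely. The sign reverses with the direction of the imbalance.

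**Precision.** The variance of an individual T1-to-T3 change is 2 × 10² × (1 − 0.6) = 80.
- Complete data: standard error √(2 × 80 / 70) = 1.51.
- 42 completers per arm only: √(2 × 80 / 42) = 1.95.
- Carried forward at 40% loss, where the 22.5% lost before T2 contribute no variance: about √(2 × 80 × 0.775 / 70) = 1.33.

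Simulation puts the SD of the valid estimator under missing at random at about 1.9. So the rule reports more precision after 40% loss than complete data would give.

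**Second set of assumptions.** With SD 8, half of the loss before T2, and effects of 2 at T2 and 4 at T3, simulation under missing at random gives 2.78 at 40% loss (95% interval coverage 78%) and 3.37 at 20% (coverage about 92%).

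**The case against.** Four stronger readings are tempting, and the protocol does not support them.

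- *That 40% of the SF-12 and ALI values at T3 will be imputed.* Section 4.6 ties the 40% to day 180, and no loss rate is given for day 70. The 40% results are therefore the upper part of a range. At 20% the bias is clearly smaller, though still present.
- *That the rule always biases the contrast.* It does not. With equal loss and a common trend, simulation shows no bias and a type I error near 5%. With an effect that wanes only partly (4 at T2, 2.5 at T3, under the SD 8 assumptions) the estimate was 2.2 to 2.3. Nor does the protocol give arm-specific loss rates, so unequal loss is plausible but not documented.
- *That the reported standard error is wrong for the carried-forward estimate.* It matches that estimate's own sampling SD (1.07 against 1.09 in the SD 8 simulation). The understatement is relative to the information actually available about T3.
- *That the protocol says drop-outs are carried forward.* The sentence speaks only of randomly missing values. Applying it to drop-outs is an inference, though a natural one given intention-to-treat and the absence of any other rule.

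These points limit the size and certainty of the bias. They do not defend the rule: the special cases in which it is harmless cannot be known in advance, so it cannot be relied on as conservative.

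**Conclusion.** The concern stands in conditional form. The stated rule can distort the primary group-by-time contrast in either direction whenever outcomes change over time, and it treats imputed values as observed. For loss of 20% to 40% by T3, a growing effect at the protocol's own relevance threshold loses roughly 15% to 30% of its size (2.1 or 1.7 against 2.5). Unequal loss with a common improvement can raise the type I error from 5% to about 6% to 10%. These sizes rest on the assumed SD, correlation, trajectories and loss pattern, none of which the protocol gives. The direction of the argument does not rest on the particular SD. The 40% figure applies directly only to the questionnaire outcomes at day 180. The rule should be changed before analysis.

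**What to change.** In section 6.3:

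1. Delete the carry-forward sentence.
2. For the T1 to T3 endpoints, make the linear mixed model on all observed values of all randomised participants, without imputation, the analysis under missing at random. It replaces the ANOVA option, which usually drops incomplete cases.
3. Where nparLD is used for non-normal outcomes, run it on all observed values without carrying forward, and report the mixed model or multiple imputation alongside it, because its validity under missing at random is not assured.
4. Add one multiple-imputation sensitivity analysis that shifts imputed intervention-arm values towards worse, defined per outcome: lower for SF-12, higher for ALI. A uniform downward shift would favour the intervention on ALI, where section 4.4.1 counts a reduction as improvement.
5. Keep carry-forward, if at all, as a supportive analysis labelled as such.

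The cost is one paragraph, a little more analysis work and a wider confidence interval.

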- b. During these hikes, participants will engage in 20 minutes of mindfulness training in a natural and safe environment.
- c. In weeks 2-5, participants may elect to embark on the hikes independently or to participate in the guided hikes.

Week 6 – Week 10 (day 36 – day 70): Self-guided

- a. 3 x 1,5-2h self-guided Green Exercise peer week (Hikes close to home according to prepared tour recommendations 3-6 km, 100-300hm)
- b. During these hikes, participants will engage in 20 minutes of mindfulness training in a natural and safe environment.
- c. In weeks 6-10, no further guided hikes will be offered; participants will be encouraged to conduct the sessions independently. During this period, participants will receive notifications to conduct the therapy sessions via the MyCap app. They will also be requested to complete the app-based questionnaire three times a week during the therapy sessions.

In weeks 11-26, participants will no longer receive reminders to complete therapy sessions. Similarly, they will no longer receive active requests to complete the app-based questionnaire.

The tour recommendations are located throughout Salzburg city to prevent repetition and promote self-determination.

The tour offers recommendations for hikes of varying difficulty levels. Following the initial guided hike, participants are classified according to their fitness level. This is achieved by measuring their heart rate during the hike using a heart rate monitor and by assessing their perceived exertion using the Borg scale (Löllgen, 2004).

The therapy sessions are documented at the location of the mindfulness training sessions using the smartphone app *MyCap*. MyCap is a free, mobile, REDCap-based application for study participants that can be installed on iOS and Android devices to collect the results reported by participants for a specific study previously created in REDCap. The integration of MyCap into REDCap provides a comprehensive and secure data collection system, which is particularly well-suited to longitudinal studies that require frequent requests for information from participants (Harris et al., 2022). The questionnaire asks about the current mood (SPANE, PRS), the perceived exertion, whether the therapy session is being conducted in a group or individually, and whether the patient used public transportation to get to the session (see also 4.4 Outcome parameters).

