6.1 Data collection

Data collection takes place at four time points: Day 1 (t1), day 35 (t2), day 70 (t3) and day 180 (see also chapter 4.5 Study timeline).

The data collection process at time points t1, t2 and t3 is almost identical. The data collection on day 180 is carried out as an online questionnaire survey. It should be noted that some data is collected only once, e.g: socio-demographics (t1), satisfaction with the intervention (t2).

As part of the initial examination (t1), all study participants will undergo a clinical assessment with the study physician on duty, who will decide whether or not the participant is eligible to participate in the study.

Data will be collected by qualified staff of the Institute of Ecomedicine at the Paracelsus Medical University and the University Clinic for Internal Medicine I at the University Hospital of Salzburg according to the following data collection plan:

- T-1 (as soon as there is a positive vote from the Ethics Committee): recruitment, randomization
- T1 resp. day 1: baseline examination
- T2 resp. day 35: examination after guided intervention
- T3 resp. day 70: follow-up examination 1
- T4 resp. day 180: follow-up examination 2

Digital data entry will be performed in a secure REDCap⁵ database system, which will be set up for the NATURE-MET-S study to securely store and process pseudonymized data. REDCap is a secure web application for building and managing online surveys and databases.

In addition, the participants will evaluate the individual therapy sessions using the Mycap mobile app⁶. The following data will be collected:

- Intervention location
- Date, time
- Connectedness to nature
- Individual or group setting
- Details of travel to the intervention location
- Self-assessed physical activity
- Photo of the surroudings (no persons!)
- Affective States (I-PANAS-SF, Perceived Restorativeness Scale (PRS))

MyCap is a freely available participant-facing mobile application that can be installed on iOS and Android devices to capture patient-reported outcomes for any REDCap project.

⁵ REDCap (project-redcap.org)

⁶ https://projectmycap.org/

MyCap's integration with REDCap provides a comprehensive data collection ecosystem and is best suited for longitudinal studies with frequent requests for information from participants (Harris et al., 2022).

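### A Shapiro-Wilk pre-test chooses between a mean-based and a rank-based analysis of SF-12 and ALI, and the interaction that decides on an effect is not tied to a defined contrast

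*Protocol*

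**What the plan says.** Section 6.3 (Check for normal distribution) sets the selector: "The Shapiro-Wilk test will be applied to check for normal-distribution. Depending on data distribution, parametric or non-parametric tests will be applied". Under Longitudinal Data analysis it names the branches. One is parametric: "For longitudinal data analysis, analyses of variance (ANOVA) or linear mixed models (LMM) are used for normally distributed data". The other is rank-based: "For non-normally distributed samples, a non-parametric analysis of variance (e.g. f1.LD.f1) is performed using the nparLD package".

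The same section says the models will contain random effects for correlation in time and space, and fixed effects for group, time and their interaction. Time is described as "time effects characterizing changes between pre- and post-intervention". The interaction is called the group contrast, and of it the protocol says: "This determines whether or not the intervention has an effect".

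Sections 3.2 and 4.4.1 place the SF-12 and ALI endpoints over T1 to T3 (days 1, 35 and 70) and do not name a deciding visit. Section 4.4.1 defines clinical relevance as 2.5 points on SF-12 and a 0.5 SD reduction in ALI.

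On the schedule, section 4.3 lists weeks 6-10 within the intervention: "3 x 1,5-2h self-guided Green Exercise peer week". Section 4.5 calls the same weeks the first follow-up phase. Section 6.1 labels T2 as "examination after guided intervention" and T3 as a follow-up examination.

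**The concern.** The two branches answer different questions. A mixed model estimates a mean difference in points or SD units. The rank method estimates a relative effect, roughly the probability that a value in one group and visit exceeds a value drawn from the pooled distribution. If trial data select the branch, nobody can say beforehand what will be estimated for either primary outcome. SF-12 and ALI could end up on different scales, and one of them on a scale to which the protocol's own relevance thresholds do not apply.

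The decision rule adds a second gap. An interaction over three visits asks only whether the two profiles differ in shape. It can be significant for a lasting benefit, a benefit gone by day 70, or harm. A pre/post contrast behaves differently, but what counts as post is unclear because weeks 6-10 carry two labels.

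**Working it through.** **1. The plan's own figure.** In the section 4.6 table, power is the number of significant runs over 1000, for example 817/1000 = 0.817 at n=40. With 40% loss, 70 × 0.6 = 42 completers per arm. Interpolating between n=40 and n=50 gives 0.817 + 0.2 × (0.873 − 0.817) = 0.828. This agrees with 70 per arm, although 42 is not a row of the table and no target power is stated. The simulation used F1-LD-F1, the rank model. The table is not disputed here, but it belongs to one of the two branches.

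**2. How the pre-test behaves.** The protocol does not give the scoring rule for ALI, so both constructions below are assumptions. ALI 1 lists 14 markers when systolic and diastolic pressure are counted separately.

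| Assumed ALI | n=42 | n=70 | n=140 |
|---|---|---|---|
| Count of 14 independent markers, 30% high-risk each | about 54% rejected | about 92% | 100% |
| Average of 14 normal z-scores | about 5% | about 5% | about 5% |

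The number of tests matters too. For truly normal data, one test per arm and visit, taken as independent, gives at least one rejection in 1 − 0.95⁶ = 26.5% of trials. One pooled test per visit gives 1 − 0.95³ = 14.3%. The protocol does not say what is tested (raw values, changes or residuals; by arm or pooled).

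**3. What the rank branch can carry.** The listed fixed effects (group, time, interaction) are the factors of an F1-LD-F1 design, so they fit. The listed random effects do not, and the output is not in points or SD.

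**4. The decision rule under both readings.** Let a and b be the group differences in change from baseline at T2 and T3, in SD units. Assume n = 42 per arm and equal within-person correlation r = 0.6.

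- 2-df interaction: λ = (n/2)(2a² − 2ab + 2b²)/[3(1 − r)] = 21(2a² − 2ab + 2b²)/1.2, F with 2 and 81 df.
- 1-df baseline versus mean of T2 and T3: λ = [(a+b)/2]² × n/[2 × 1.5(1 − r)] = 35[(a+b)/2]².
- 1-df baseline-adjusted T3 difference: λ = b² × n/[2(1 − r²)] = 32.8b².

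| Pattern (a, b) | 2-df: λ, power | Pre/post: λ, power | T3 only: λ, power |
|---|---|---|---|
| Day 35 only (0.5, 0) | 8.75, 74% | 2.19, 31% | 0, 5% |
| Sustained benefit (0.5, 0.5) | 8.75, 74% | 8.75, 83% | 8.20, 81% |
| Sustained harm (−0.5, −0.5) | 8.75, 74% | 8.75, 83% | 8.20, 81% |
| Reversal (0.5, −0.2) | 13.65, 91% | 0.79, 14% | 1.31, 20% |
| Building (0.25, 0.5) | 6.56, 61% | 4.92, 59% | 8.20, 81% |
| Fading (0.5, 0.25) | 6.56, 61% | 4.92, 59% | 2.05, 29% |

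Simulations of the day-35-only pattern agree: 72 to 76% for the 2-df test (72% for its rank-based counterpart) and about 30% for pre/post. The first three rows have the same λ under the 2-df test, so significance alone cannot tell them apart.

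Sensitivity of the day-35-only row: for r from 0.4 to 0.8, the 2-df power runs from 55% (λ = 5.83) to 97% (λ = 17.5) and pre/post from 22% to 54%. With all 70 per arm at r = 0.6, λ = 14.58 and the 2-df power is 93%.

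**The case against.** A reader might infer more than the protocol supports, and these objections stand:

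- **The deciding test is an omnibus test.** The text does not say so. That reading follows from three visits plus f1.LD.f1, while the wording speaks of pre and post. A single contrast is at least as literal, and it roughly halves the day-35-only figure or better (74% to 31%).
- **ALI will almost certainly fail the normality test.** That holds for an assumed count score. For averaged normal z-scores the rejection rate is 5%.
- **The test is run on raw values rather than residuals.** The protocol does not state what is tested.
- **The pre-test inflates the false-positive rate.** In simulation, each interaction test on its own rejected in about 5 to 7% of null trials. This gives no sign of gross inflation.
- **Direction is lost altogether.** Section 3.2 asks about improvement and section 4.4.1 defines an ALI reduction. A mixed model can yield visit-specific differences, and direction can be read from relative effects. However, the stated rule requires neither.
- **Day 70 must be the sole primary time point.** That is a trade-off: it gains power for a building effect (81% against 61%) and loses it for a fading one (29% against 61%).
- **The schedule sections contradict each other on dates.** They do not. The T2 label fits the end of guided hikes in week 5. Only the description of weeks 6-10 differs.

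It can also be said that contrasts and effect measures are commonly left to the analysis plan. That excuses missing detail. It does not excuse a selection rule and a decision rule that the protocol itself fixes.

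**Conclusion.** The point holds in a bounded form and should be corrected. The protocol makes a Shapiro-Wilk result choose the analysis of the primary outcomes. On the rank branch there is no mean difference to set against 2.5 points or 0.5 SD, and the stated random effects are not fitted. How often that branch is taken cannot be known from the protocol: the assumed ALI scores span about 5% to 92% at n=70.

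On the decision rule, the conclusion is conditional. If the interaction is tested over T1 to T3, an effect of 0.5 SD confined to day 35 is significant in about 72 to 74% of trials. If it is one pre/post contrast, the figure is about 30%. Both assume 42 per arm and r = 0.6. The 42 applies loss assumed up to day 180 to a day-70 endpoint, so retention may be better. The fault is an unsettled estimand and a conclusion that is hard to interpret, with no demonstrated loss of type I error control.

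**What to change.** 1. Remove the normality test as selector. Pre-specify one linear mixed model for SF-12 and ALI whatever their distribution, with residual checks and robust or bootstrap standard errors if needed. Keep nparLD as a sensitivity analysis.
2. Replace the statement that the interaction decides with a named group contrast, reported as an adjusted mean difference with 95% CI and read against the 2.5-point and 0.5 SD thresholds. Report the differences at T2 and T3 in any case. The sponsor should choose the deciding time point or average, given the trade-off shown above.
3. Reconcile section 4.3 with sections 4.5 and 6.1 on whether weeks 6-10 and T3 are intervention or follow-up, so that post-intervention has one meaning.

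Items 1 to 3 are changes of wording, with no added data collection. The real cost is in section 4.6: its power table was simulated for F1-LD-F1, so it must be re-run for the new primary model or described as approximate for it.
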